3.3.2.1 Use errors

Like entertainment video games, the investigational device requires minimal knowledge, experience, education, and training in its use. Necessary training is included in the installation

manual and in-game tutorials. Ergonomic factors in the usage environment can affect realisation of adverse effects originating from joint pain and tension which is why we guide the subject to pay attention to their ergonomics. The subjects are instructed to set up an environment where excessive strain on back, neck and wrists are minimised.

3.3.2.2 Device stress under normal operating conditions

The device comprises client software at the subject's personal computer and backend software at the sponsor's backend servers.

The backend server capacity is sized to handle 100 times more concurrent patients than expected at any moment of this clinical investigation, and hence, under normal operating conditions, the backend stress is very unlikely to contribute to net device stress and its risk of failure.

The client software may face performance limitations depending on the CPU and GPU capacity of the subject's personal computer. When running in computers meeting the minimum specification, the client's performance is adequate to achieve the device's intended treatment outcome.

Device stress under normal operating conditions does not adversely affect the health or safety of the subject or any other persons.

3.3.2.3 Chemical, physical and biological properties and interaction

Investigational device is a software thus it does not possess chemical, physical or biological properties hence it does not react to environmental materials and substances. No particles can be released to the subject's body.

3.3.2.4 Substance labelling

The investigational device has no substances thus it does not require such labelling.

3.3.2.5 Compatibility

The investigational device's client application, *i.e.*, the "game" installed on the subject's personal computer, is compatible with the Windows operating system and a wide variety of hardware components as long as the minimum requirements are met. To ensure compatibility, it is advised to use a modern (purchased after 2010) computer with a separate graphics processing unit (GPU). Using an incompatible computer may lead to a compromised user experience or altogether prevent the playing of the game, but it does not cause any risks for the subject's health or safety.

Minimum requirements:

- CPU: Intel or AMD Quad-Core
- RAM: 4 GB
- OS: Windows 7
- VIDEO CARD: GeForce GTX 260 (1 GB) or Radeon HD 4850 (1 GB)

3.3.2.6 Consequent risks

Fault conditions regarding the investigational device do not produce any consequent risks for subjects' health or safety.

3.3.2.7 Diagnostic or measuring functions

The device does not have diagnostic functions. The device has measuring functions for the subject's cognitive performance evaluation and adaptation of the game to the subject's individual performance level and changes therein. The measuring functions are designed in such a way that they are not compromised by usage of low performing personal computers as long as the minimum requirements are met.

3.3.2.8 Power shortage

Power shortage regarding the back-end server or on-site operating computer prevents access to the software but it does not cause any risks for the subject's health or safety.

3.3.2.9 Clinical parameters

The investigational device does not have clinical parameters; hence parameters going out of range can not lead to death or severe deterioration, thus there are no alarm systems.

3.3.2.10 Electromagnetic interference

Investigational device being a software, it does not produce electromagnetic interference (EMI) or is affected directly by environmental EMI thus achieving intrinsic immunity to it. Subject's operating computer produces and is affected by EMI in quantities defined by the manufacturer of the operating computer.

3.3.2.11 Unauthorised access

Signing in to the distribution platform (Steam) requires a personal login account and the game client requires another login account. Considering that the device is operated at the subject's home, these procedures provide adequate levels of unauthorised access prevention. Also, the subjects are informed that they are not to give access to other people as explained in Appendix 3 (Salassapitovelvoite ja käyttöoikeus).

Back-end servers are in secure data centre facilities with multiple security layers and access control.

3.3.2.12 Protection against mechanical and thermal risks

The investigational device is a software, thus it is not directly affected by mechanical, vibrational or thermal energy which could lead to risks for the subject.

3.3.2.13 Noise emission

The investigational device is software, thus it does not directly generate noise other than the audio components of the gameplay. The player can control the volume, turn it off, or use headphones at their discretion.

3.4 Relevance of the clinical investigation

MDD is a considerable, global public health problem that causes considerable personal suffering for the subjects and is a leading cause of disability worldwide.

Medical relevance: Depression is, at worst, lethal. In 2015, there were 788 000 people who died due to suicide (WHO, 2017), and suicide is the cause of 1.5% of deaths globally. Out of all suicides, two thirds are related to depression, and when depression is related to suicide, the subject hasn't often had proper treatment for the disorder (Depressio, Käypä hoito). Thus, developing the existing treatment, treatment pathways, and creating new treatments that can also help reach underserved populations can help treat depression.

Economical relevance: MDD causes considerable economic burden to societies. Globally, depression led to *“a total of over 60 million years lived with disability”* only in 2015, according to WHO (2017). In Europe, the annual cost of MDD is €100B, approximately one eighth of the costs of all brain disorders together and one half of the cost of cancer. In the United States, the annual cost of MDD is \$200B.

To address this global mental health challenge, it is thus vital to not only improve existing treatments but to develop novel complementary approaches that leverage the benefits of the digital therapeutics and yield highly-scalable and low-cost treatments.

3.5 Objectives and hypotheses of the clinical investigation

Main objective

The primary objective of this research is to assess the effectiveness of MEL-T01 in reducing MDD symptoms. The subjects are randomised into three research arms (MEL-T01, MEL-S01, and TAU), and their subject health questionnaire (PHQ-9) scores are measured on five occasions (see Table 1).

Research arms

- MEL-T01
- MEL-S01
- TAU

Time intervals

- T0, before subjects in MEL-T01 and MEL-S01 arm begin the active intervention.
- T1, 4 weeks after T0
- T2, 8 weeks after T0

- T3, 12 weeks after T0
- T4, 24 weeks after T0

Primary hypotheses

- MEL-T01 is superior to TAU in alleviating MDD symptoms as measured by the change in subject health questionnaire (PHQ-9) score between time points T0 (before the intervention) and T3 (after a 12-week intervention).
- MEL-S01 is superior to TAU in alleviating MDD symptoms as measured by the change in PHQ-9 score between T0 and T3.
- MEL-T01 superior to MEL-S01 as measured by the change in PHQ-9 score between T0 and T3.

Secondary hypotheses

- In terms of a score change from T0 to T3,
MEL-T01 is superior to TAU,
and MEL-S01 is superior to TAU,
and MEL-T01 superior to MEL-S01 in:
 - reducing depression symptoms as measured by quick inventory of depressive symptomatology (QIDS),
 - reducing rumination as measured by short-version ruminative response scale (RRS),
 - reducing anxiety symptoms as measured by general anxiety disorder (GAD-7),
 - reducing the disability symptoms as measured by sheehan disability scale (SDS),
 - increasing positive emotions as measured by positive valence systems scale (PVSS),
 - and
 - improving well-being as measured by the WHO-five well-being index (WHO-5)
- The effect of the MEL-T01 is mediated by the training dose, as measured by the subject's total game-playing time during the intervention, and evidenced by a positive correlation between MEL-T01 game time and reduction in symptoms as measured by the PHQ-9.
- The effect of the MEL-S01 is mediated by the training dose, as measured by the subject's total game-playing time during the intervention, and evidenced by a positive correlation between MEL-S01 game time and reduction in symptoms as measured by the PHQ-9.

- The effects of MEL-T01 on depressive symptoms as measured by PHQ-9 are mediated by positive game experience as measured by the immersive experiences questionnaire (IEQ).
- The effects of MEL-S01 on depressive symptoms as measured by PHQ-9 are mediated by positive game experience as measured by the immersive experiences questionnaire (IEQ).

Exploratory hypothesis

- The effects of the MEL-T01 and MEL-S01 on MDD symptoms are sustained in the follow-up period as measured by the change of PHQ-9 scores between T3 and T4.
- The effects of MEL-T01 and MEL-S01 will also emerge in the TAU group once as measured by the change of PHQ-9 between T3 and T4.
- The MEL-T01, MEL-S01, and TAU cohorts are equal in how they are treated for depression over the intervention period aside from the intervention.
- Interventions MEL-T01 and MEL-S01 are not significantly associated with an increase from T0 to T3 in game addiction as measured by the 7-item game addiction scale (GAS).
- The effects of the MEL-T01 and MEL-S01 on depressive symptoms as measured by PHQ-9 are (negatively) mediated by substance abuse as measured by ASSIST-LITE.
- The effects of MEL-T01 and MEL-S01 on depressive symptoms as measured by PHQ-9 are mediated by PTSD symptoms as measured by PTSD checklist for DSM-5 (PCL-5).
- The effects of MEL-T01 and MEL-S01 on depressive symptoms as measured by PHQ-9 are mediated by experiential avoidance as measured by the brief experiential avoidance questionnaire (BEAQ).

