The subjects ($N = 800$) volunteering to participate in this investigation are diagnosed with MDD and have an on-going mental health treatment contact with a mental health professional. The subjects are recruited through Helsinki and Uudenmaan sairaanhoitopiiri (HUS) psychiatry and Varsinais-Suomen sairaanhoitopiiri (VSSHP) psychiatry as well as online.

The subjects are randomised into three arms with equal probabilities in blocks of six consecutive subjects. Subjects in the MEL-T01 and MEL-S01 arms are engaged in the intervention for 12 weeks while those in the TAU arm are on a follow-up period during these 12 weeks.

After this 12-week period, the subjects in MEL-T01 and MEL-S01 arms enter a 12-week follow-up period and the subjects in TAU arm engage with either the MEL-T01 or MEL-S01 intervention (randomised at T0 with equal probability) for 12 weeks (See Table 1 below).

The subjects are recommended to play the investigational-device game for a total of 48 hours during the 12 weeks of active intervention with a recommended weekly dose of 4 hours. A minimum of 24 hours is needed for inclusion to hypothesis testing. The subjects are limited to a daily maximum of 1.5 hours of game time.

Prior to the intervention, a clinical interview (MINI) is performed via phone to confirm the subject's MDD diagnosis. The subjects' mental health symptoms and well-being are evaluated through online questionnaires five times: before subjects are randomised into one of the three groups (T0), and then 4 (T1), 8 (T2), 12 (T3), and 24 (T4) weeks after the study has begun.

Subject population:**Criteria for inclusion:**

Eligible subjects must fulfil all of the following criteria:

1. Between 18-65 year-old
2. Suffering from major depressive disorder
3. Have an ongoing mental health treatment contact to basic healthcare, specialised healthcare, student healthcare or occupational healthcare
4. Has sufficient eyesight with or without prescription
5. Has a Windows computer with internet connection and mouse
6. Has email and phone number

Criteria for exclusion:

Subjects who fulfil any of the following criteria are excluded from the study:

1. They have threat of self-harm
2. They have addiction to digital games
3. They have psychotic disorders
4. They are pregnant or breastfeeding
5. They have impaired ability in decision making
6. They are prisoner or forensic subject
7. They have neurological disorders such as epilepsy or brain injury

Safety assessments:

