3.6.4 Measures to minimise bias

3.6.4.1 Blinding

In order to ensure minimum bias, the main study is double-blinded so that neither the subjects nor the investigators, CSCs in particular, know whether any given subject is randomised to the MEL-T01 or MEL-S01 study arm. Investigators are aware of which subjects are randomised to the TAU arm but will be blinded to the subsequent intervention of the TAU-arm subjects with MEL-T01 or MEL-S01 after their initial follow-up period has ended.

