3.6.4.2 Randomisation

The recruited MDD subjects are randomised into the MEL-T01, MEL-S01, and TAU arms in blocks of six consecutive subjects so that two subjects are allocated into each arm and so that one subject in the TAU arm will receive MEL-T01 and the other TAU subject MEL-S01 at the end of their initial 12-week follow period.

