3.15 Criteria and procedures for follow-up

3.15.1 Subjects following the end

The MEL-T01 and MEL-S01 have a 12 week follow-up period after the playing intervention between T3 and T4. TAU has a playing period between T3 and T4.

All subjects are emailed after they have filled the T4 questionnaire when the study period ends for all of the groups. In this email, the subjects are told about the randomisation as well as which group they belonged to as explained in Appendix 2 (Participant information and consent form). The subject is informed that the research results will be published later. The

subject is asked for feedback regarding the study, and their questions regarding the study are answered. The subject is thanked for their participation. The subject is asked for feedback regarding the study, and their questions regarding the study are answered via email or phone.

The subject is compensated for their participation based on Social and health ministry 82/2011 §2: 50€ if they have played the game for at least 24 hours and answered all questionnaires; or 120€ if they have played the game at least 48 hours and answered all questionnaires.

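### The exploratory T3–T4 hypotheses (effects emerging in TAU, effects sustained in the device arms) rest on PHQ-9 changes with no comparator or margin and should be reported as descriptive only

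*Combined protocol and SAP*

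**What the plan says.** Section 3.5, repeated in the synopsis (3.1.6), lists two T3–T4 hypotheses under the exploratory heading. For the TAU arm, device effects "will also emerge in the TAU group once as measured by the change of PHQ-9 between T3 and T4". For the two device arms, effects "are sustained in the follow-up period as measured by the change of PHQ-9 scores between T3 and T4". No comparison group is named for either, and no amount of worsening is defined that would count as loss of effect.

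On what happens after T3, section 3.15.1 states that "TAU has a playing period between T3 and T4", while the MEL-T01 and MEL-S01 arms are in follow-up. The synopsis says that "the subjects in TAU arm engage with either the MEL-T01 or MEL-S01 intervention (randomised at T0 with equal probability) for 12 weeks". Section 3.6.4.2 balances this second allocation within each block of six: "one subject in the TAU arm will receive MEL-T01 and the other TAU subject MEL-S01 at the end of their initial 12-week follow period". Section 3.6.4.1 adds that investigators "will be blinded to the subsequent intervention of the TAU-arm subjects with MEL-T01 or MEL-S01 after their initial follow-up period has ended".

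Section 3.7.3 sets out tests for primary and secondary objectives only, and its change scores start at T0. No stated hypothesis or test uses the second-phase allocation of the TAU arm.

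**The concern.** Words such as emerge and sustained attribute a change, or the absence of one, to the device. The measure named cannot carry that attribution. TAU subjects must have an ongoing treatment contact to enter the trial, so a fall in PHQ-9 while they play mixes any device effect with continuing care, natural recovery and expectation. In the device arms, a small T3–T4 change does not show maintenance without a margin, and recovery under usual care could mask the loss of a device effect.

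The protocol uses the same reasoning against others. Section 3.2.10.7 faults an earlier digital-intervention study in depression for having neither a comparator nor a control group, so that its improvement could have been ongoing recovery.

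At stake is the wording of the exploratory results. A report that follows the stated measure could present background improvement as a device effect. Meanwhile a randomised comparison that the design already contains would go unreported.

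**Working it through.** **1. The plan's own figure.** Section 3.7.4.1 gives d = 0.40, two-sided alpha 0.05/3 = 0.0167, power 0.80 and 133 per arm. The normal approximation n = 2(z₁₋α/₂ + z₁₋β)²/d² gives 131. The exact two-sample t calculation gives 132.2, rounded up to 133, with power 0.803 at that size. The figure reproduces. The documents give no sample size or power for any T3–T4 hypothesis.

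**2. Who is off the game between T3 and T4?**

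| Arm | T0–T3 | T3–T4 |
|---|---|---|
| MEL-T01 | plays | follow-up after playing |
| MEL-S01 | plays | follow-up after playing |
| TAU | no game | plays MEL-T01 or MEL-S01 |

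No group that has never had a game remains alongside the TAU subjects who are playing.

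**3. What a within-group test would show with no device effect.** Let δ be the background T3–T4 improvement in SDs of the change score. The documents do not give δ, so it is an assumption shown as a range. For a one-sample t-test at two-sided 0.05, the chance of a significant result in the direction of improvement is P(T > 1.978), where T is noncentral t with 132 df and noncentrality δ√133.

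| δ (assumed) | Noncentrality | Chance of significant improvement |
|---|---|---|
| 0 | 0 | 2.5% |
| 0.1 | 1.15 | 21% |
| 0.2 | 2.31 | 63% |
| 0.3 | 3.46 | 93% |
| 0.4 | 4.61 | 99.6% |

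**4. What the randomised contrast inside TAU can deliver.** Splitting 133 TAU subjects 1:1 gives 133/2, about 66 per device. Power comes from a two-sample t-test with noncentrality 0.40√(n/2) at two-sided 0.05. Sizes below 66 are assumptions about how many are analysable at T4. The smallest, 33, halves the group, in line with the 50% dropout that section 3.7.4.1 assumes.

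| n per device | Noncentrality | Power |
|---|---|---|
| 66 | 2.30 | 0.63 |
| 50 | 2.00 | 0.51 |
| 40 | 1.79 | 0.42 |
| 33 | 1.62 | 0.36 |

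With 66 per device, 80% power needs d = 0.49. About 100 per device would be needed at d = 0.40.

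**5. Combining both phases.** Stratifying by phase gives about 133 + 66 = 199 per device, or 133 + 33 = 166 if half the TAU subjects are lost after T3. At d = 0.40 and two-sided 0.0167 the power would be 0.94 or 0.89. Both figures assume the same effect and SD in the two phases.

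**The case against.** The strongest objection is that MEL-T01 versus MEL-S01 does not answer either hypothesis. Section 3.2.12.2 expects both games to have positive effects. If both work equally well the contrast is null, and if neither works it is also null. The same holds for the two device arms at T4: a zero difference fits both effects lasting and both effects vanishing. This stands in full. A reader might infer that the unused randomisation would rescue the claim about TAU. The documents do not support that, because no game-free group remains after T3. The contrast is worth adding for the question it does answer, the difference between the games.

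Second, these are two exploratory lines, one of them garbled, with no test, alpha or decision rule attached. That also stands. The plan does not say that a within-group test will be run or that a non-significant change will be called maintenance, so the error rates above illustrate a risk and do not describe a stated procedure. What remains is that the stated measure has no comparator and nothing elsewhere supplies one.

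Third, other references exist: the TAU arm's own game-free T0–T3 period, and the device arms, which are off the game during T3–T4. Either can give context. Neither is a concurrent untreated control, since the first is earlier in the course of illness and care and the second has already had 12 weeks of play.

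Fourth, the power of the within-TAU contrast depends on how many TAU subjects reach T4 after starting self-guided play at T3. This stands, and is why 0.36 belongs beside 0.63. The plan also does not say how the 24-hour play rule in section 3.7.2 applies to TAU after T3. Applying it would select on behaviour after the switch and weaken the randomised comparison.

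**Conclusion.** The point holds for the exploratory T3–T4 hypotheses. As measured, neither can distinguish a device effect from ongoing recovery and usual care, and the claim of a sustained effect also lacks a margin. The false-attribution figures of 21% to 99.6% rest on an assumed background improvement of 0.1 to 0.4 SD, 133 TAU subjects with T3 and T4 scores, and a within-group test that the plan does not spell out.

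Two stronger readings should be resisted. One is that the trial's main result is undermined: the primary and secondary hypotheses on score change use T0–T3 and have their own between-arm tests, so they are not touched. The other is that pooling both phases lifts the primary power to 0.94. That figure belongs to a supportive estimate under a same-effect, same-SD assumption, while the primary analysis keeps its planned power of 0.80.

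The blinding text on the second-phase device names investigators. That TAU subjects are also blind to which game they receive is inferred from the general blinding statement in section 3.6.4.1.

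**What to change.** 1. Report within-arm T3–T4 PHQ-9 changes with confidence intervals as descriptive, and do not conclude from them that an effect emerged or was sustained. Reword the two hypotheses in sections 3.1.6 and 3.5 to match.
2. Add an exploratory analysis of MEL-T01 versus MEL-S01 within the TAU arm: T4 PHQ-9 adjusted for T3 PHQ-9, by assigned second-phase device, without selecting on play time after T3, reported with a confidence interval. State that it tests the difference between the games and not either game against no game, and give its power as about 0.63 with 66 per device and 0.36 with 33.
3. Report the MEL-T01 and MEL-S01 arms at T4, as change from T0, as a between-device comparison and not as proof of maintenance.
4. Optionally, add a stratified estimate combining both phases, labelled supportive, with its same-effect and same-SD assumption stated.

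The cost is SAP wording and one or two exploratory models; the data are already collected, since PHQ-9 is scheduled at T3 and T4 for all arms. The loss is the uncontrolled claim of a device effect in TAU.

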3.3.1.2 Anticipated AEs

In guidelines for good clinical practice E6(R2) European medicines agency defines adverse events (AE) as: *“Any untoward medical occurrence in a patient or clinical investigation subject administered a pharmaceutical product and which does not necessarily have a causal relationship with this treatment.”*

The subjects may have unanticipated or anticipated adverse events during the study. Below, we have identified anticipated AE that may arise in the use of the MEL-T01 or MEL-S01 software. The list is based on possible negative events that may occur from playing entertainment video games (see Playstation, 2022) that closely resemble the MEL-T01 and MEL-S01 software. The adverse events are:

- Frustration
- Boredom
- Stress
- Eye ache
- Headache
- Dizziness
- Nausea
- Neck pain

- Visual disturbances
- Migraine
- Muscle twitching
- Uncomfortable feelings or ache in hands
- Losing sense of time and space

We take measures to mitigate the anticipated AE. We guide the user to pay attention to ergonomics, ensure sufficient lighting, and keep breaks while playing. Should the user encounter any AE, they are guided to stop playing, and report the AE to the researchers either through the in-game link or email. The information to the subjects is included in Appendix 2 (Tutkittavan tiedote) and the information given to the subject is found in Appendix 6 (Investigator's brochure). For AE reporting procedures, see [3.14](#).

Another risk is the potential addiction that video games may create. To mitigate this risk, we take the following precautions: 1) Digital game addiction is an exclusion criteria for the study. 2) We only recommend playing 45 minutes per day, and the players cannot play the game for more than 90 minutes per day at which point the game locks them out. 3) Our game doesn't include highly addictive features such as so-called loot boxes.

"A very small percentage of individuals may experience epileptic seizures or blackouts when exposed to certain light patterns or flashing lights." (Playstation, 2022). Considering the risk for epileptic seizure, we exclude subjects who have a history of epilepsy from the study to mitigate the risk. We also inform the subject about this (see Appendix 6 - Investigators brochure, 2.2.5.).

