For the secondary endpoints, we sought to use clinical outcome measures that describe comprehensively the complex symptomatology of MDD. To corroborate our results with our primary outcome measurement, PHQ-9, we also employ another depression questionnaire (QIDS). As Finnish Käypä Hoito recommendation mentions, many patients that suffer from depression also suffer from anxiety (measured in our study by GAD-7), and we evaluate the potential of the interventions to influence symptoms of anxiety. Depression is also associated with rumination (measured in our study by RRS), that we hypothesise our intervention may reduce. Anhedonia, or the lack of positive emotions associated with depression (measured in our study by PVSS) may also be influenced. We also examine how depression influences disability in the subject’s everyday life (as measured by SDS) and measure the subjects’ general well-being (as measured by WHO-5). We also predict that the impact of our game is mediated by the degree the player immerses themselves into the game (as measured by IEQ).

Finally, the exploratory endpoints assess the post hoc comparability of patient cohorts and seek to identify factors mediating intervention success. These include substance abuse (as measured by ASSIST-LITE), post-traumatic stress disorder (measured in our study by PCL-5), and experiential avoidance, tendency to avoid negative experiences (measured in our study by BEAQ). We also evaluate whether the interventions influence game-addiction (measured in our study by GAS). For details regarding the clinical questionnaires, see section 3.6.5.1.

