3.7.3 Hypothesis tests and multiple comparisons

Primary and secondary objectives in this clinical study are to demonstrate a statistical difference on outcome measure mean change scores between the following groups:

1. MEL-T01 and MEL-S01
2. MEL-T01 and TAU
3. MEL-S01 and TAU

We will first assess whether we use a parametric or non-parametric test.

- Using the Shapiro-Wilk test we explore if MEL-T01, MEL-S01, and TAU model residuals are normally distributed regarding PHQ-9.
- Using Levene's test we test whether the variance of MEL-T01, MEL-S01 and TAU model residuals are equal regarding PHQ-9.
- If both tests are $p > 0.05$, we will use a repeated measures Linear Mixed Model; If either test is $p < 0.05$, we will use a repeated measures Linear Mixed Model with robust standard errors.
- For primary endpoint evaluation (PHQ-9), we will conduct a one-tailed test for the arm pairs MEL-T01-vs.-MEL-S01, MEL-T01-vs.-TAU, and MEL-S01-vs.-TAU. We

are using a significance level of 0.05. Using Holm-Bonferroni correction, we find the multiple-comparison corrected $p = 0.05/3 = 0.0167$.

Change scores are defined as the scores obtained between the pre-intervention (T0) assessment and the during/post-intervention assessments. The general formulation of the null and alternative hypotheses are

$$H_0: \mu_x = \mu_y$$

$$H_1: \mu_x \neq \mu_y$$

where H_0 is the null hypothesis, H_1 is the alternative hypothesis and $x, y \in \{A, B, TAU\}$, $x \neq y$.

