3.7.4 Power and sample size

3.7.4.1 Power analysis

A power analysis was conducted to determine appropriate sample size for the study to detect a statistical difference between change scores for the primary hypothesis in a two tailed, repeated measures t-test. Assuming that our samples are independent and identically distributed with normal distribution (see [3.7.3](#)), we analyse the required sample size as follows:

- We conduct sample size analysis using G*Power 3.1.9.7
- We use a two-tailed t-test.
- Cohen (1988) suggests a small effect size is 0.20 and medium effect size is 0.50. As a point of comparison, a meta-analysis of internet-based treatments for adult depression have reached an average effect size of 0.41 (Anderson & Cuijpers, 2009). Meanwhile, Motter et al. (2016) found in their meta-analysis that computerised cognitive training had an effect size of 0.43 on depression symptom severity. Thus, we use an effect size $d = 0.40$.
- We use an alpha error probability of 0.0167 that corresponds to an alpha level of 0.05 with Bonferroni correction for the three primary endpoint tests.
- We use power of 0.80
- We allocate subjects equally to the three arms, leading to allocation ratio of 1:1:1

This leads to a total sample size of 133 per arm and with three arms this equals 399 subjects, which we round to **400 subjects** that we aim to have in T3.

Karyotaki et al. (2015) explored the dropout in self-guided web-based interventions for depression using different psychotherapeutic approaches. While their approach is based on psychotherapies, and ours on cognitive training, the medium of training is the same

(web-based), the intervention is self-guided, and they target people with depression. Karyotaki et al. found that in 10 RCTs 59% of the subjects dropped out before completing half the treatment modules.

Meanwhile, Torous et al. (2020) explored dropout rates for app interventions for depression. Considering publication bias, they found a dropout rate of 47.8%.

Considering the above, we assume a dropout rate of 50%. Thus, we aim to recruit up to 400 subjects / 0.50 = 800 subjects to begin the study.

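### The exploratory game-addiction hypothesis can be met by a non-significant GAS result, with no margin or confidence-interval rule behind it

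*Combined protocol and SAP*

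**What the plan says.** Among the exploratory hypotheses in section 3.5, repeated in synopsis section 3.1.6, is "Interventions MEL-T01 and MEL-S01 are not significantly associated with an increase from T0 to T3 in game addiction", measured by the 7-item GAS. Section 3.6.1 describes the same analysis neutrally: "We also evaluate whether the interventions influence game-addiction (measured in our study by GAS").

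Game addiction is one of the plan's own risks. Section 3.3.1.2 says "Another risk is the potential addiction that video games may create", and Table 2 rates it probable before mitigation, possible after it, and of moderate severity.

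The testing section, 3.7.3, does not reach this hypothesis. Its scope is "Primary and secondary objectives in this clinical study are to demonstrate a statistical difference on outcome measure mean change scores" between arm pairs. Nothing there or elsewhere in section 3.7 gives the GAS hypothesis a contrast (within arm or against TAU), an alpha, an analysis set, a margin or an interval rule. Sample size in 3.7.4.1 is set for PHQ-9 alone.

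A neighbouring exploratory hypothesis says that the three "cohorts are equal in how they are treated for depression over the intervention period aside from the intervention". It names no measure, test or margin.

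**The concern.** A hypothesis that asserts non-significance reverses the burden of proof: the smaller or noisier the sample, the easier it is to satisfy. For a superiority endpoint, low power works against the sponsor's claim. Here it works for the claim.

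This is the only hypothesis in the plan that addresses the addiction risk. If the wording is followed, the report could say that the devices were not associated with an increase when the data could not exclude one that matters. A reader would take that as a safety finding.

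**Working it through.** **Inputs from the plan.** Analysed number per arm: "This leads to a total sample size of 133 per arm and with three arms this equals 399 subjects" (3.7.4.1). Alpha for PHQ-9: "We use an alpha error probability of 0.0167 that corresponds to an alpha level of 0.05 with Bonferroni correction", two-tailed in 3.7.4.1, whereas 3.7.3 tests one-tailed. Planned recruitment: 800 over three equal arms, 800/3 ≈ 266 per arm.

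**Assumptions, because the plan is silent.** Effects are in SD units of the T0 to T3 GAS change score, with equal SDs across arms. The base case is one device against TAU, 133 per arm, two-sided 0.05. Other alphas, contrasts and sample sizes are shown as a range.

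**Step 1: the plan's own figure.** Two-sample t-test, noncentrality d/√(2/n). With d = 0.40, n = 133 and two-sided 0.0167, power is 0.803 (n = 132 gives 0.799). The 133 per arm is reproduced, for PHQ-9 superiority.

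**Step 2: chance that a true GAS increase is non-significant.** √(2/133) = 0.1226, so the noncentrality is 0.2/0.1226 = 1.63, 0.3/0.1226 = 2.45 and 0.4/0.1226 = 3.26, on 264 degrees of freedom.

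| True increase against TAU | Two-sided 0.05 | One-sided 0.05 | Two-sided 0.0167 |
|---|---|---|---|
| 0.2 SD | 63% | 51% | 78% |
| 0.3 SD | 32% | 21% | 48% |
| 0.4 SD | 10% | 5% | 20% |

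At two-sided 0.05, a miss is more likely than not only below about 0.24 SD.

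**Step 3: more favourable readings of the plan (two-sided 0.05).**
- Within-arm T0 to T3 test, n = 133, noncentrality d√133: missed 37% at 0.2 SD and 7% at 0.3 SD.
- Device against TAU with GAS data from all of about 266 per arm: also 37% and 7%. This is a best case, since 3.7.4.1 assumes 50% dropout.
- Both devices pooled against TAU, 266 v 133: 53% and 20%.

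**Step 4: what a non-significant result leaves open.** The 95% CI half-width at 133 per arm is 1.96 × 0.1226 = 0.24 SD. An estimate just short of significance has an upper limit of about 2 × 0.24 = 0.48 SD. At 266 per arm the half-width is 1.96 × √(2/266) = 0.17 SD and that limit is 0.34 SD.

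**Step 5: what a margin rule would deliver.** With no true difference, the chance that the upper 95% limit falls below a margin M equals one-sided 0.025 power at d = M. At 133 per arm it is 37% for M = 0.2 SD, 68% for 0.3 SD and 90% for 0.4 SD. For 80%, n per arm = 2(1.960 + 0.842)²/M², which is 393, 175 and 99.

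**The case against.** The strongest reply is that this is one exploratory bullet. No rule says a non-significant GAS result will be reported as proof of safety, and section 3.6.1 words the analysis neutrally. The addiction risk is managed by exclusion, the daily play limit, design features and adverse-event reporting, not by this hypothesis. All of that stands and lowers the consequence. It does not repair the wording: the hypothesis in 3.5 is still met by a non-significant result, and the neutral sentence in 3.6.1 supplies no rule to use instead.

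It can also be said that the contrast, alpha and sample behind any miss rate are the reviewer's choice. That is correct, and it is why Steps 2 and 3 give a range.

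Three stronger readings are tempting, and the documents do not support them.
- A reader might infer that a real increase would usually go unreported. That holds only for small increases. At 0.3 SD against TAU it would be detected more often than not in every scenario above, and at 0.4 SD 80% to 95% of the time. GAS points are never tied to SD units, so no figure here is shown to be clinically relevant.
- A reader might infer that the equal-treatment hypothesis makes the same error. It contains no significance wording and no decision rule. What it lacks is a measure and a margin, which is a different and lesser fault. Nor does the PHQ-9 interpretation rest on it: the plan relies on block randomisation and on blinding between the two devices.
- A reader might take the GAS threshold in 3.6.5.2 as a ready cut-off for counting new cases. It is an interview rule, used when the coordinator is uncertain, and the coordinator may apply a lower one.

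**Conclusion.** The point holds for the game-addiction hypothesis. As written, absence of significance would count in favour of no increase in a named risk, and no margin or interval rule prevents that.

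Assuming device against TAU with 133 per arm, a true increase of 0.2 SD would satisfy the hypothesis 63% of the time (51% to 78% across the alpha and sidedness choices). For 0.3 SD it is 32% (21% to 48%), and for 0.4 SD 10% (5% to 20%). A within-arm test, or GAS data from about 266 per arm, lowers the first two to about 37% and 7%. The contrast, alpha, analysis set and SD scale are all assumptions.

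The hypothesis is exploratory, so no primary conclusion is affected. The change is still worth making, because the statement concerns safety and the correction needs no new data. The equal-treatment hypothesis needs clearer wording only.

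**What to change.** - In 3.5 and the synopsis, replace the absence-of-significance wording with estimation: the MEL-T01 minus TAU and MEL-S01 minus TAU differences in T0 to T3 GAS change, each with a 95% CI, in all randomised subjects with GAS data. State this in 3.7.3 and align 3.6.1 with it.
- Fix a margin in advance, in GAS points, with a justification. Conclude no relevant increase only if the upper limit is below it. Otherwise report the estimate and interval without a safety conclusion.
- If subjects newly above a GAS threshold are counted by arm, apply one fixed cut-off to the scheduled GAS form, not the discretionary interview rule in 3.6.5.2.
- Summarise depression treatment received by arm, with between-arm differences and CIs, and drop the claim of equality.

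Cost: a few lines of text and one justified margin. By section 3.7.1.2, GAS is already collected at T0 to T4 and treatment status at T1 to T4. The downside is that the statement is harder to earn: with a 0.2 SD margin and 133 per arm, truly harmless devices would each earn it only 37% of the time.
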